2. SAMPLE SIZE CONSIDERATION

No formal sample size calculation is performed for this extension study. A sample size of approximately 390 is based on the estimated maximum number of subjects who might be expected to continue from the ALK3831-A305 study.

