3. DATA ANALYSIS

3.1. General Statistical Methodology

Baseline for efficacy or safety analysis is defined as the last non-missing assessment before the first dose of ALKS 3831 in ALK3831-A306 study, and it will be used for all efficacy and safety analysis unless specified otherwise.

Antecedent study baseline, defined as the last non-missing assessment on or before the first dose of study drug during double-blind treatment period in ALK3831-A305 study, may be explored as applicable.

Treatment sequence is defined according to the treatment assignment in antecedent and current studies as ALKS 3831/ALKS 3831 (ALKS 3831 in both ALK3831-A305 study and ALK3831-A306 study), OLZ/ALKS 3831 (olanzapine in ALK3831-A305 study and ALKS 3831 in ALK3831-A306 study), or PBO/ALKS 3831 (placebo in ALK3831-A305 study and ALKS 3831 in ALK3831-A306 study).

In general, descriptive statistics: n, mean (\pm standard deviation [SD]), median, minimum, and maximum, for continuous variables and number and percentage of subjects in each category for categorical variables will be provided.

All statistical tests and confidence intervals (CIs), unless stated otherwise, will be 2-sided and will be set at an alpha level of 0.05.

All source data will be presented as subject data listings.

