3.8. Efficacy Analyses

3.8.1. General Considerations

All statistical analysis will be performed at the 5% significance level. All confidence intervals (CI) will be 2-sided 95% confidence intervals. Efficacy analysis will be carried out using the FAS population. PANSS total and subscale scores, CGI-S, PANSS response analyses and body weight will be based on both observed data and the LOCF (last observation carried forward) imputation, that is, the last observed non-missing postbaseline value will be carried forward for missing postbaseline assessments.

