3.8.2. Efficacy Analysis

The following endpoints will be used to evaluate durability of treatment effect and summarized by treatment sequence and overall for FAS population:

- Change from baseline in PANSS total score, and subscale scores (positive, negative, and general psychopathology subscales) by visit
- Change from baseline in PANSS Excited Component (EC) score (comprised of 5 items, P4. excitement, G4. tension, P7. hostility, G8. uncooperativeness, and G14. poor impulse control) by visit
- Change from baseline in PANSS Marder factor scores by visit
- Change from baseline in CGI-S by visit
- Proportion of Subjects with PANSS response ($\geq 30\%$ improvement from baseline in PANSS total score)
- Time to first relapse
- Time to first remission
- Time to discontinuation

In general, continuous and categorical endpoints will be summarized using descriptive statistics by treatment sequence and overall. Change from baseline within the treatment sequence and overall may also be tested using an one-sample t-test.

The PANSS Marder factor model² consisted of the following 5 factors:

- Negative symptoms
 - N1. blunted affect
 - N2. emotional withdrawal
 - N3. poor rapport
 - N4. passive social withdrawal
 - N6. lack of spontaneity
 - G7. motor retardation
 - G16. active social avoidance
- Positive symptoms
 - P1. delusions
 - P3. hallucinatory behavior
 - P5. grandiosity
 - P6. suspiciousness
 - N7. stereotyped thinking
 - G1. somatic concern
 - G9. unusual thought content
 - G12. lack of judgment and insight
- Disorganized thought
 - P2. conceptual disorganization
 - N5. difficulty in abstract thinking
 - G5. mannerisms and posturing
 - G10. disorientation
 - G11. poor attention
 - G13. disturbance of volition
 - G15. preoccupation
- Uncontrolled hostility/excitement
 - P4. excitement
 - P7. hostility

- G8. uncooperativeness
- G14. poor impulse control
- Anxiety/depression
 - G2. anxiety
 - G3. guilt
 - G4. tension
 - G6. depression

Stabilization is defined as meeting all of the following stabilization criteria:

- PANSS total score ≤ 80
- PANSS score ≤ 4 on each of the following items:
 - P2: conceptual disorganization
 - P3: hallucinatory behavior
 - P6: suspiciousness
 - G9: unusual thought content

After a subject achieves stabilization, relapse and remission are defined as following:

- Relapse: $\geq 30\%$ increase in PANSS total score or re-hospitalization for psychotic symptoms.

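### The optional one-sample t-test of change from baseline cannot show durability, and its pooled overall form mixes maintained effect with placebo subjects' response to starting active drug

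*SAP*

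**What the plan says.** SAP 3.8.2 introduces its efficacy endpoints, including change from baseline by visit in PANSS and CGI-S, with this statement: "The following endpoints will be used to evaluate durability of treatment effect and summarized by treatment sequence and overall for FAS population". It commits to descriptive statistics by sequence and overall, then adds the only test it names: "Change from baseline within the treatment sequence and overall may also be tested using an one-sample t-test". It states no null value.

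SAP 3.1 fixes the reference point: "Baseline for efficacy or safety analysis is defined as the last non-missing assessment before the first dose of ALKS 3831 in ALK3831-A306 study". Protocol Table 3, footnote b, agrees, taking the final A305 visit as the baseline. The same SAP section defines three sequences: ALKS 3831 in both studies, olanzapine then ALKS 3831, and "PBO/ALKS 3831 (placebo in ALK3831-A305 study and ALKS 3831 in ALK3831-A306 study"). The A305 baseline is also defined, but its use is only exploratory.

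On error level, SAP 3.1 says "All statistical tests and confidence intervals (CIs), unless stated otherwise, will be 2-sided and will be set at an alpha level of 0.05", and SAP 3.8.1 says "All statistical analysis will be performed at the 5% significance level". SAP 3.8.4 marks multiplicity as not applicable. Protocol 14.5 plans descriptive statistics only for PANSS and CGI-S, so the t-test is an addition in the SAP.

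**The concern.** The test's null does not match the question in two ways.

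1. **Within ALKS 3831/ALKS 3831.** Baseline falls after four weeks on the drug. An effect that is exactly maintained has mean change zero, which is the null. Rejection means further improvement or loss. Non-rejection excludes neither, and taken alone it says nothing about how much worsening is compatible with the data.
2. **Overall.** In PBO/ALKS 3831, change from the A306 baseline is onset of response to active drug. Averaging this with maintenance in the two treated sequences gives a quantity that is neither. It can be significantly favourable when subjects already on active drug have not changed, or have worsened.

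At stake is a P value, shown among analyses meant to address durability, that a reader could take as evidence of a lasting or growing effect when it reflects placebo subjects starting treatment.

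**Working it through.** The plan has no figure to reproduce. SAP section 2 reports no sample size calculation, and on the number it says: "A sample size of approximately 390 is based on the estimated maximum number of subjects who might be expected to continue". The documents give no SD, effect size, sequence split or dropout rate.

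**Inputs from the documents:** N about 390; two-sided alpha 0.05; A306-entry baseline; three sequences pooled as overall.

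**Assumed inputs:** placebo-switcher fraction f of 1/3, 1/4 or 1/5; within-sequence SD of PANSS change s of 10, 15 or 20; switcher mean change d of −5, −10 or −15 (negative is improvement); mean change w in the treated sequences of 0, 1 or 2. N=200 and 260 were also tried.

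**Pooled test.**
- Pooled mean = (1 − f)w + f·d.
- Pooled SD = √[s² + f(1 − f)(d − w)²].
- Noncentrality = pooled mean / (pooled SD/√N).
- P(significant improvement) is taken from the noncentral t. At N=390 the critical value is 1.966.

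Main example (f=1/3, w=0, d=−5, s=15):
- mean = −5/3 = −1.67
- SD = √(225 + (2/9)·25) = 15.18
- noncentrality = −1.67/(15.18/√390) = −2.17
- P(significant improvement) ≈ Φ(2.17 − 1.97) ≈ 0.58

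The nominal rate in that direction is 0.025.

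Treated sequences worsening (f=1/3, w=2, d=−10, s=15):
- mean = (2·2 − 10)/3 = −2.0
- SD = √(225 + (2/9)·144) = 16.03
- noncentrality = −2.46
- P(significant improvement) ≈ 0.69; with w=1 it is 0.91

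Sensitivity at N=390:

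| Switcher fraction | Switcher change | Others | SD | P(overall significantly improved) |
|---|---|---|---|---|
| 1/3 | −5 | 0 | 10 | 0.89 |
| 1/3 | −5 | 0 | 15 | 0.58 |
| 1/3 | −5 | 0 | 20 | 0.37 |
| 1/4 | −5 | 0 | 15 | 0.37 |
| 1/5 | −5 | 0 | 15 | 0.26 |
| 1/3 | −10 | 0 | 15 | 0.99 |
| 1/5 | −10 | 0 | 15 | 0.72 |
| 1/3 | −10 | +2 | 15 | 0.69 |
| 1/4 | −10 | +2 | 15 | 0.24 |

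With the treated sequences at zero, the range over all assumed settings (N 200 to 390, SD 10 to 20) is 0.10 to 1.00. At N=390 and SD 15, with no observed change elsewhere, an observed switcher change of about −4.5 (one third switchers) to −7.6 (one fifth) is enough to make the overall result significant.

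**Test within ALKS 3831/ALKS 3831** (assumed n = 390/3 = 130, SD 15):
- Standard error = 15/√130 = 1.32.
- True change 0: P>0.05 in 95% of trials, at any n.
- True worsening of 2 points: noncentrality 2/1.32 = 1.52; P>0.05 in 67%.
- True worsening of 3 points: noncentrality 3/1.32 = 2.28; P>0.05 in 38%.

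A non-significant result is therefore common both when the effect is kept and when some of it is lost. The 95% CI has half-width 1.98 × 1.32 = 2.6 points and shows directly how much worsening the data allow.

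**The case against.** The case for leaving the text alone is substantial.

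- **The test is optional and secondary.** The SAP says change may be tested. The sole objective is long-term safety, and there is no sizing and no efficacy hypothesis. A reader might infer that the sponsor will rest a durability claim on this P value. The documents do not say so.
- **Durability is addressed elsewhere.** A reader might infer that the plan has no proper durability analysis. It does: SAP 3.8.2 includes Kaplan-Meier time to first relapse (after stabilization) and time to discontinuation, both by sequence, plus by-visit descriptives. It also leaves open use of "Antecedent study baseline, defined as the last non-missing assessment on or before the first dose of study drug during double-blind treatment period in ALK3831-A305 study". From that baseline, zero change in ALKS 3831/ALKS 3831 would mean that the earlier gain had gone, so the first mismatch would not arise.
- **A pooled result would sit beside its components.** In simulated trials with the treated sequences at zero and a significant overall improvement, PBO/ALKS 3831 was itself significantly improved in 78–100% and ALKS 3831/ALKS 3831 in only 3–9%. The driver would usually be visible.
- **The planned summaries already give n, mean and SD by sequence,** from which a CI can be derived.

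These arguments reduce the likely harm and set the severity. They do not make the test informative. By-sequence display helps with the pooling problem but not with the null, because the by-sequence test has the same null. An optional test in an open-label study also leaves the decision to report it open until the data have been seen.

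A further tempting step is to require a maintenance margin. The documents contain no efficacy hypothesis on which to base one, and the study is an unsized, uncontrolled extension, so the point does not need it.

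**Conclusion.** The concern holds as a modest point (CONSIDER). It follows from the SAP's own definitions that zero change is the pattern of maintained effect in ALKS 3831/ALKS 3831, and that the overall test combines maintenance with onset of response. Neither conclusion needs an outside figure.

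The size does. The 58% in the main example assumes N=390, SD 15, one third placebo switchers improving 5 points and no change in the others; plausible alternatives move it widely. The N=390 cases take the planned maximum, and fewer observed subjects lower the figure: the same example at N=200 gives 34%.

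Two stronger statements go too far. A maintained effect does not always give P>0.05: that holds in 95% of trials, and only if mean change is exactly zero; continued improvement on drug would give a significant result. Nor can it be said that a significant overall result will come from the placebo switchers, only that it can.

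**What to change.** In SAP 3.8.2, replace the t-test sentence with:

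> Mean change from baseline will be presented with its two-sided 95% CI by treatment sequence. Change in PBO/ALKS 3831 will be described as response to starting active treatment. The overall column will be descriptive only, without a test, and will not be used to support durability.

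Durability is then read from the by-sequence intervals in subjects already on active drug (ALKS 3831/ALKS 3831, with OLZ/ALKS 3831 shown separately), together with the planned relapse and discontinuation analyses. No margin is required.

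The cost is SAP and table-shell wording; no new data or visits are needed, and SAP 3.8.1 already sets two-sided 95% intervals. The downside is that the pooled P value is lost and the durability statement rests on fewer subjects with wider intervals. Under the assumed equal split and SD 15, the half-width is about 2.6 points at n=130, against 1.966 × 15/√390 = 1.5 points for 390 pooled subjects.

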14.5. Efficacy Analysis

Efficacy analyses will be carried out using the FAS Population. The following endpoints will be used to evaluate durability of treatment effect:

- Change from Baseline in PANSS total score and subscales by visit
- Change from Baseline in CGI-S by visit
- PANSS response
- Relapse
- Remission
- Time to discontinuation

The PANSS (total and subscale scores) and CGI-S scores, and appropriate changes from Baseline, will be summarized using descriptive statistics. Positive and Negative Syndrome Scale response and remission at each visit will be summarized as number and percentage.

The discontinuation rate and the relapse rate will be estimated using the Kaplan-Meier (KM) Method and the KM plot will be provided.

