- Remission: PANSS score ≤ 3 (mild or less) on each of the following items in two consecutive efficacy assessments
 - P1: delusions
 - G9: unusual thought content
 - P3: hallucinatory behavior
 - P2: conceptual disorganization
 - G5: mannerisms/posturing
 - N1: blunted affect
 - N4: social withdrawal
 - N6: lack of spontaneity

Time to first relapse will be estimated using the Kaplan-Meier method by treatment sequence and overall. It is defined as the time from the date of stabilization to the date of first relapse. Subjects who completed the treatment without relapse will be censored at the date of last dose. Time to first remission will be analyzed similarly.

Time to treatment discontinuation will be analyzed similarly using the Kaplan-Meier method by treatment sequence and overall. Both all cause discontinuation and discontinuation due to AE will be summarized. For prematurely discontinued subjects (all cause or due to AE), time to event is defined as time from the date of first dose of study drug to the date of last dose of study drug. Other subjects will be censored at the last dose of the study drug.

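### Time to first remission carries a full-analysis-set label but is defined and timed only from stabilization, and the protocol's by-visit remission counts are missing from the SAP

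*SAP*

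**What the plan says.** **Population.** SAP 3.8.2 opens its endpoint list with "The following endpoints will be used to evaluate durability of treatment effect and summarized by treatment sequence and overall for FAS population". Time to first relapse and time to first remission are on that list. Under SAP 3.2.2 a treated subject joins the FAS with a single PANSS after baseline; stabilization is not required.

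**Events.** "Stabilization is defined as meeting all of the following stabilization criteria": PANSS total of 80 or less, and P2, P3, P6 and G9 each at 4 or less. Then: "After a subject achieves stabilization, relapse and remission are defined as following". Relapse is a 30% or greater "increase in PANSS total score or re-hospitalization for psychotic symptoms". Remission is a score of 3 or less on eight named items at two successive assessments. P6 and the total score are not part of it.

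**Clock.** For relapse: "It is defined as the time from the date of stabilization to the date of first relapse". For remission: "Time to first remission will be analyzed similarly". Time to discontinuation is also handled by analogy, but the SAP gives it its own origin, the first dose. Remission gets no such override.

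**Protocol.** Protocol 14.5, which uses the FAS, plans that PANSS "response and remission at each visit will be summarized as number and percentage". The SAP list contains PANSS response as a proportion, but remission only as a time to event. SAP 5 declares no major deviation from the protocol's analysis.

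**The concern.** A never-stabilized FAS subject has no start date for either curve and, as the definitions stand, can have neither event. The population named for the endpoint and the rule that defines it do not fit together. For remission this matters because subjects who never stabilize are likely to remit less often. Leaving them out gives the probability of remission among the stabilized, which a reader of the table would take as a rate for the whole FAS.

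Remission is one of the durability endpoints, and results are shown by treatment sequence. PBO/ALKS 3831 subjects enter after a 4-week antecedent treatment period on placebo, so the share who never stabilize may differ between sequences. Curves conditioned on stabilization would then describe differently selected groups, and no planned table shows how many subjects stabilized in each.

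**Working it through.** The documents state no stabilization, remission or relapse rate, and the 390 planned subjects come from no formula (SAP 2). There is no figure of the plan to reproduce; the percentages below are assumptions.

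**1. Formula.** Let u be the share of the FAS never stabilized, r the remission share among the stabilized, and q the share of never-stabilized subjects who meet the eight-item rule.

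- FAS rate = (1 − u)r + uq
- Gap = r − FAS rate = u(r − q)

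The gap is positive whenever r > q, and for given u and r it is largest, ur, at q = 0.

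**2. Upper bound.** Take r = 60%, q = 0, an FAS of 390, and SE = √[0.6 × 0.4 / (390(1 − u))].

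| u | FAS rate, 0.60(1 − u) | Gap, 0.60u | SE of the 60% |
|---|---|---|---|
| 5% | 57% | 3 points | 2.5 points |
| 10% | 54% | 6 points | 2.6 points |
| 20% | 48% | 12 points | 2.8 points |
| 30% | 42% | 18 points | 3.0 points |

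At u = 20% and q = 0, moving r from 30% to 70% moves the gap from 6 to 14 points. At u = 0 there is no gap.

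**3. Can q exceed zero?** Yes, because meeting the eight-item rule does not imply stabilization. Eight items at 3 sum to 24. If the other 22 items sum to 57 (57/22 = 2.6 on average), the total is 81, above the limit of 80. A subject with P6 at 5 also fails stabilization while free to meet all eight remission items. Such a subject is barred from remission only if stabilization is missed at every assessment up to that point, not at one visit. With q = 20% instead of 0, the gaps in the table fall to u × 0.40, that is 2, 4, 8 and 12 points.

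**4. Dependence on the unwritten rule.** A simulation of 20,000 subjects per setting assumed 50% remission by day 336 among the stabilized, 35% leaving early, and stabilization at day 0 (60%) or day 28 (40%). Kaplan-Meier remission at day 336:

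| Never-stabilized subjects | 80% stabilized | 60% stabilized |
|---|---|---|
| Excluded | 0.502 | 0.504 |
| Censored at time zero | 0.502 | 0.504 |
| At risk from first dose, censored at last dose | 0.401 | 0.300 |
| Kept event-free to day 364 | 0.385 | 0.279 |

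The last two rows need a start date that SAP 3.8.2 does not give to never-stabilized subjects. At 80% stabilized, the choice of rule moves the estimate by 0.502 − 0.385 = 0.117, about 12 points.

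**The case against.** The SAP names the FAS and states no exclusion, so loss from the denominator is an inference. That is right: a reader might take exclusion as a written rule, and it is not. The defect is a risk set that the stated origin cannot supply for part of the named population. Exclusion is simply what a programmer would most naturally do.

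A reader might also infer that psychotic worsening in never-stabilized subjects is counted nowhere. The documents do not support that. Such worsening is absent from the relapse endpoint only. PANSS and CGI-S change cover the whole FAS. All-cause and adverse-event discontinuation run from first dose, and reasons for discontinuation are tabulated (SAP 3.3, 3.8.2). Protocol 13.2 makes hospitalization for behavioral-health worsening a serious adverse event, and SAP 3.9.1 tabulates those events.

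It is tempting to call never-stabilized subjects certain non-remitters and r(1 − u) the true rate. Step 3 shows that some could meet the item rule, so the tabulated gaps are upper bounds for their assumed r and u. They also treat a Kaplan-Meier estimate as a simple proportion and ignore dropout. Enrollees completed the antecedent treatment period and were judged able to benefit (Protocol 7.1), so u may be small. At 5% the gap is at most 3 points, about one standard error.

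Gating relapse on prior stability is a coherent definition. Counting never-stabilized subjects as non-events would lower the relapse rate, not correct it. Remission among the stabilized is also a legitimate quantity if labelled as such. Finally, Protocol 14.5 does not define remission, and Protocol 14.2 leaves details to the SAP, so the silence on stabilization there proves little. The omission of the by-visit counts is the firmer point, and nothing in the SAP answers it.

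**Conclusion.** The point holds in this form. The gate and the time origin in SAP 3.8.2 cannot yield a remission rate for the FAS, and the protocol summary that would have given one is not on the SAP's list. On the natural reading the Kaplan-Meier estimate is conditional on stabilization and lies above the FAS rate if stabilized subjects remit more often than the rest. With r = 60% the excess is at most about 3 to 18 points for 5% to 30% never stabilized, and smaller if barred item-level remitters are counted. Both ranges are assumptions. A statement that the remission rate is overstated by a known amount would go beyond the documents.

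The change should be made, but it does not touch the primary objective, which is safety. The efficacy summaries are mainly descriptive, and no test is planned on remission or relapse.

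**What to change.** In SAP 3.8.2:

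1. Restore remission as n (%) at each visit with all FAS subjects as denominator, applying the eight-item criterion without the stabilization precondition. Say to which visit the two-assessment criterion is credited.
2. Measure any FAS time to remission from the first A306 dose.
3. Keep the stabilization-based Kaplan-Meier curve for relapse and, if wanted, for remission, but label each as among stabilized subjects.
4. Print n (%) ever stabilized by treatment sequence and overall beside those curves, and say whether stabilization may be met at baseline.

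All of this uses data already collected. The cost is SAP wording, a few extra table rows, and a remission figure that may be less favourable.

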7.3. Subject Withdrawal

A subject may be discontinued from the study at any time if the subject, Investigator, or the Sponsor determines that it is not in the best interest of the subject to continue participation. If a subject has an absolute neutrophil count (ANC) $< 1.0 \times 10^3$ per µL or HbA1c $\geq 6.5\%$ at any time during this extension study, the subject will be discontinued from the study. Other reasons for discontinuation include the following:

- AEs
- Lack of Efficacy
- Lost to follow-up
- Withdrawal by subject

- Protocol Deviation (noncompliance with study drug or study procedures)
- Pregnancy
- Study terminated by Sponsor
- Other

If a subject withdraws from the study for any reason, any ongoing AEs will be followed until resolution, until deemed stable by the Investigator, or until the subject is deemed by the Investigator to be lost to follow-up. If, in the opinion of the Investigator, it is necessary to monitor a subject beyond the Safety Follow-up Visit, the Follow-up Period may be extended, as necessary. In such instances, the Sponsor and the Investigator will agree to an acceptable follow-up schedule.

In the event that a subject chooses to withdraw from the study, the Investigator should make a reasonable effort to ascertain the reason(s) for withdrawal, while fully respecting the subject's rights. Enrolled subjects are to be asked to return to the clinic for an Early Termination (ET) Visit and to complete a subsequent Safety Follow-up Period. The ET Visit should be scheduled as close as possible to the subject's last dose and will mimic the assessments scheduled to be conducted at the End of Treatment (EOT) Visit (Visit 28, Table 3). If the subject fails or refuses to return to the study center, an attempt must be made to contact the subject by telephone in order to assess as many safety and efficacy parameters as possible. All data collected over the telephone must be documented and kept in the subject's record.

The Investigator must maintain a record of all subjects who fail to complete the study. The reason for study discontinuation will be documented and entered on the appropriate electronic case report form (eCRF). If a subject is lost to follow-up, a reasonable attempt to contact the subject must be made and documented.

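### The relapse curve has no censoring rule for stabilized subjects who leave early, and withdrawal for lack of efficacy is not an event; censoring these leavers at last dose would likely under-estimate relapse

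*SAP*

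**What the plan says.** SAP 3.8.2 first requires stabilization and then defines relapse by two components: a 30% or greater "increase in PANSS total score or re-hospitalization for psychotic symptoms". Of time to first relapse it says: "It is defined as the time from the date of stabilization to the date of first relapse". The censoring rule that follows is: "Subjects who completed the treatment without relapse will be censored at the date of last dose". It says nothing about stabilized subjects who stop early without relapse.

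The next paragraph, on time to treatment discontinuation, says: "Other subjects will be censored at the last dose of the study drug". That sentence belongs to a different endpoint, whose clock starts at first dose. For discontinuation, "Both all cause discontinuation and discontinuation due to AE will be summarized"; no curve is planned for lack of efficacy.

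Protocol 7.3 lists "Lack of Efficacy" among the reasons for discontinuation. It also asks early leavers to attend an ET visit, close to the last dose, which "will mimic the assessments scheduled to be conducted at the End of Treatment (EOT) Visit (Visit 28, Table 3". Table 3 in Protocol 8.2 schedules a PANSS at that visit. The fallback in Protocol 7.3 is: "If the subject fails or refuses to return to the study center, an attempt must be made to contact the subject by telephone".

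**The concern.** A stabilized subject who stops because the drug no longer works is close in meaning to a relapse, but the SAP does not count that withdrawal as one. If such a subject is censored at last dose, Kaplan-Meier assumes the same later relapse risk as in comparable subjects who stay on treatment. That is hard to believe for someone who left because of treatment failure, so the censoring is likely informative and the curve likely too favourable.

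The missing rule is a second problem. Until it is written, a programmer could censor these subjects, keep them at risk to Week 52 or drop them, and each choice gives a different relapse estimate. At stake is one of the endpoints meant to show durability of effect over 52 weeks.

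**Working it through.** **Step 1. Who is covered.** Setting SAP 3.8.2 against Protocol 7.3 and Table 3:

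| Stabilized subject | Status in the relapse curve |
|---|---|
| Completes without relapse | Censored at last dose |
| Stops early; meets the PANSS or re-hospitalization criterion by ET | Event, but the SAP does not say whether an ET PANSS dated after last dose counts |
| Stops for lack of efficacy; ET PANSS up by less than 30%; not re-hospitalized | Not an event; no rule |
| Stops for lack of efficacy; no ET PANSS (for example telephone contact only); not re-hospitalized | Not an event; no rule |
| Stops for another reason without relapse | No rule |

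**Step 2. How a failure can escape.** PANSS is scheduled at Weeks 4, 8, 12, 24, 36 and 52/ET, so the gaps after Week 12 are 12, 12 and 16 weeks. The ET visit brings the next PANSS forward. The spacing therefore matters mainly when the ET PANSS is missing, because the last score may then be months old. The unscheduled visits in Protocol 8.2 cover drug return, adherence review and dispensing, not PANSS.

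A 30% rise can also be a high bar. The SAP does not name the reference score; taking the score at stabilization, a subject at the limit of 80 must reach 80 × 1.3 = 104. The bar is not uniformly strict, since a subject at 60 relapses at 60 × 1.3 = 78, which is still within the stabilization limit of 80.

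**Step 3. Illustration.** The documents state no relapse or withdrawal rate, so there is no planned figure to reproduce. All rates below are assumptions. Take constant, independent hazards over 52 weeks from stabilization, with net probabilities:

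- R = 10%, relapse by the SAP criteria: r = −ln(0.90) = 0.1054
- L = 5%, lack-of-efficacy withdrawal: l = −ln(0.95) = 0.0513
- O = 30%, other withdrawal: o = −ln(0.70) = 0.3567
- h = r + l + o = 0.5133, so exp(−h) = 0.90 × 0.95 × 0.70 = 0.5985
- f = share of lack-of-efficacy leavers who meet the relapse criteria by ET

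Formulas for 52-week relapse:

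- Leavers censored at last dose: 1 − exp(−(r + f·l))
- Lack of efficacy counted as an event: 1 − exp(−(r + l))
- Leavers kept at risk to Week 52: CI = ((r + f·l)/h) × (1 − exp(−h))
- Non-relapsing leavers excluded: CI/(CI + exp(−h))

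With f = 0:

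- Censored: 1 − 0.90 = 10.0%
- Counted: 1 − 0.90 × 0.95 = 14.5%
- Kept at risk: (0.1054/0.5133) × 0.4015 = 8.2%
- Excluded: 0.0824/(0.0824 + 0.5985) = 12.1%

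| Handling of leavers | f = 0 | f = 0.5 | f = 1 |
|---|---|---|---|
| Kept at risk to Week 52 | 8.2% | 10.2% | 12.3% |
| Censored at last dose | 10.0% | 12.3% | 14.5% |
| Excluded | 12.1% | 14.6% | 17.0% |
| Lack of efficacy counted as event | 14.5% | 14.5% | 14.5% |

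Censoring instead of counting lowers the estimate by 14.5 − 10.0 = 4.5 points at f = 0, by 14.5 − 12.3 = 2.2 at f = 0.5, and by nothing at f = 1.

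**Step 4. Range.** Over R = 5% to 20% and L = 2% to 10%, the gap is 1.6 to 9.5 points at f = 0, 0.8 to 4.6 points at f = 0.5, and zero at f = 1. The extremes at f = 0 are 21.6 − 20.0 (R = 20%, L = 2%) and 14.5 − 5.0 (R = 5%, L = 10%).

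**The case against.** The strongest reply is that the exit visit is itself a PANSS visit. A subject leaving for lack of efficacy is due a PANSS at ET and is a relapse if the rise is large enough. Re-hospitalization for psychotic symptoms also counts, and Protocol 13.2 requires hospitalization for worsening behavioral health to be reported as a serious adverse event. A reader might infer from the definition that treatment failures never count as relapses. The documents do not support that, and how many would be missed cannot be known from them.

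These withdrawals also stay visible elsewhere. They are events in the all-cause discontinuation curve, SAP 3.3 tabulates disposition by reason, and SAP 3.8.1 carries the last PANSS and CGI-S values forward. Relapse is one of eight unranked durability endpoints in SAP 3.8.2, in an open-label study whose only stated objective is safety and tolerability. Calling it the main durability analysis would go too far.

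Finally, PANSS rise or re-hospitalization is a coherent prespecified endpoint. Withdrawal for lack of efficacy is an open-label judgement and may reflect too little improvement rather than worsening. Adding any event type raises the estimate, so the higher figure describes a different composite and is not a corrected relapse rate.

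All of this stands, and it argues against replacing the main curve. It does not supply the missing rule, and it does not cover leavers with no ET PANSS or a sub-threshold rise. An all-cause curve or a disposition count does not show how far the relapse estimate depends on them.

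**Conclusion.** The gap is real and modest. The relapse analysis is not fully specified for early leavers, and the part of the treatment-failure group that does not qualify at ET can drop out of the event count. If these subjects are censored at last dose, which is the natural extension of the completer rule, the censoring is likely informative and relapse is likely under-estimated.

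A reader might conclude outright that durability is overstated. The documents do not establish that, because the direction depends on the rule the SAP omits. Relative to censoring, excluding leavers raises the estimate (12.1% against 10.0% at f = 0), while keeping them at risk lowers it (8.2%).

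The size cannot be computed from the documents. The gaps shown rest on assumed rates, constant independent hazards and an unknown f. They measure how far two treatments of the same leavers differ, not the bias against a true relapse rate. The matter does not touch the safety objective, and the correction is a cheap improvement.

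**What to change.** In SAP 3.8.2:

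1. Give one censoring rule for every stabilized subject without relapse, completers and leavers alike. The last-dose date already used for completers can be extended to leavers.
2. State that a qualifying ET PANSS counts as an event even when it is dated after the last dose.
3. Keep the PANSS/re-hospitalization curve as the main one. Add a sensitivity Kaplan-Meier curve that counts withdrawal after stabilization for lack of efficacy, or for an adverse event of worsening psychosis, as an event on the last-dose date.

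The cost is a few lines of SAP text and one more curve; withdrawal reasons, dosing dates and adverse events are already collected. The sensitivity figure will be no more favourable than the main one, and may include some subjects with insufficient improvement rather than true relapse. The report should say so beside the curve.
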